#### **11.4.2 Laboratory test**

The baseline laboratory test is defined as the most recent test before the first administration.

The quantitative parameter of hematology, blood biochemistry, and urinalysis in each cohort at baseline, the laboratory test result after treatment, the change from the baseline, and the normal/abnormal change from the baseline will be summarized by visit. The hematology, blood biochemistry, and urinalysis of each cohort will be summarized by the normal/abnormal changes before and after treatment.

All laboratory test results will be listed by subject ID, among which, abnormal values will be marked and indicated for clinical significance (if any).

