	
■ Safety analysis 
The AEs, SAEs, and adverse drug reactions will be analyzed mainly using descriptive statistics. Laboratory tests that are normal before the study but become abnormal after starting treatment will be described.
 
■ PK analysis 
PK analysis is performed based on the PK analysis set. PK concentrations and PK parameters (maximum and minimum concentration) are summarized by descriptive statistics. Apart from the statistics listed in the general analysis, PK concentration and PK parameter data (maximum and minimum concentration) will be also summarized descriptively using geometric mean (GM), coefficient of variation (CV%), and geometric CV% (GCV%).
 
The correlation between drug exposure and toxicity is analyzed based on the maximum and minimum concentration of SHR-1210 and apatinib.
 
■ Immunogenicity analysis 
The immunogenicity will be analyzed based on the ADA analysis set. The concentration of anti-SHR-1210 antibodies (ADAs) will be analyzed using descriptive statistics. Treatment-emergent adverse events may be analyzed separately in the ADA-negative and ADA-positive groups.

--	---

SCHEDULE OF ACTIVITIES

Study Procedures	Screening Period		Cycle 1	Cycle 2 and beyond	End of Treatment/ Withdrawal	Follow-Up Period (at the end of treatment)	
	D-28 ~ D-1	D-7 ~ D-1	D1 ± 3 ^[22]	D1 ± 3		Safety Follow-Up ^[23]	Survival Follow-Up ^[24]
Signing of Informed Consent Form ^[1]	×						
Demographics	×						
Medical History and Treatment History ^[2]	×						
Verification of Eligibility		×					
ECOG PS ^[3]		×	×	×	×	×	
Vital Signs ^[4]		×	×	×	×	×	
Physical Examination ^[5]		×	×	×	×	×	
Virology ^[6]	×						
Hematology ^[7]		×	×	×	×	×	
Urinalysis ^[8]		×	×	x ^[8]	×	×	
Fecal Occult Blood Test ^[9]		×		x ^[9]	×	×	
Clinical Chemistry ^[10]		×	×	×	×	×	
Coagulation Function ^[11]		×	×	×	×	×	
Thyroid Function ^[12]		×	×	x ^[12]	×	×	
12-Lead ECG ^[13]		×	×	×	×	×	
Echocardiography ^[14]		×			×		

Study Procedures	Screening Period		Cycle 1	Cycle 2 and beyond	End of Treatment/ Withdrawal	Follow-Up Period (at the end of treatment)	
	D-28 ~ D-1	D-7 ~ D-1	D1 ± 3 ^[22]	D1 ± 3		Safety Follow-Up ^[23]	Survival Follow-Up ^[24]
Pregnancy Test ^[15]		x			x		
Oncology Imaging Examination ^[16]	x			x ^[16]	x ^[16]	x ^[16]	x ^[16]
Study Treatment ^[17]			x	x			
Blood Sampling for PK Study ^[18]			x ^[19]	x ^[19]	x	x	

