- [12] Thyroid function: Thyroid stimulating hormone (TSH), free tri-iodothyronine (FT3), and free thyroxine (FT4). If FT3 and FT4 are unavailable, T3 and T4 can be used instead. The thyroid function is evaluated within 7 days prior to the first dose, before drug administration on Day 1 of every two cycles, at the end of treatment/upon withdrawal, and upon the first visit during the safety follow-up period.

- [13] 12-Lead ECG: Attention should be paid to QT, QTc, and PR-intervals. Performed within 7 days prior to the first dose, on Day 1 of each cycle before administration (retest is not required prior to the first dose if ECG is completed within 7 days prior to the first dose at screening), at the end of treatment/study withdrawal, and at the first visit during the safety follow-up period.
- [14] Echocardiography: Echocardiography is performed within 7 days prior to the first dose and at the end of treatment/upon withdrawal if clinically indicated.
- [15] Pregnancy test: Serum pregnancy test will be performed for women of childbearing potential. The serum pregnancy test is performed within 72 h prior to the first dose and at the end of treatment/upon withdrawal.
- [16] Tumor imaging evaluation: CT or MRI of the chest, abdomen, and pelvis. Brain MRI is required when brain metastasis is suspected and confirmed (if MRI is contraindicated, CT can be used instead). Bone scan is performed only when clinically indicated and must be performed within 42 days before the first dose.
 - ✓ At screening, tumor evaluations up to 4 weeks before the first dose and before signing the informed consent may be used as long as they meet the RECIST 1.1.
 - ✓ During the treatment period, imaging examination is performed once every two cycles (6 weeks) in the first 12 months (the first 16 cycles), then once every 3 cycles (9 weeks) thereafter. Imaging examination should be also performed if new lesions are suspected. Imaging examination should be performed when subjects withdraw from the study for any reason (\pm 4 weeks; the imaging examination does not need to be repeated if the time from the last examination is no more than 4 weeks). Imaging conditions should be the same as those at baseline (including slice thickness and contrast agent). The time window for tumor evaluation is \pm 7 days. Additional tumor evaluations may be performed if PD is suspected (for example, worsening of symptoms).

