2.2 Study Endpoints

Primary endpoint:

- Objective response rate (ORR).

Secondary endpoints:

- Progression free survival (PFS);
- Duration of response (DoR);
- Disease control rate (DCR);
- Incidence and severity of adverse events (AEs) and serious adverse events (SAEs), vital signs, ECG, and laboratory abnormalities.

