7.2 Safety Evaluation

7.2.1 Safety endpoints

Safety parameters for this study include clinical symptoms, vital signs, physical examination, laboratory tests (hematology, urinalysis, blood biochemistry, thyroid function, and coagulation function). AEs are evaluated according to NCI CTCAE Version 4.03, including type, incidence, severity, start and end date, whether it is an SAE, causality with the study drugs, and outcome.

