8.4.3 Safety analysis

The safety analysis is based on the safety set (by actual treatment received). According to Hengrui's Standard Reporting Procedures, safety will be only summarized using descriptive statistics, including but not limited to the following. The specific analysis is described in the statistical analysis plan:

- ◆ Subject disposition and populations;
- ◆ Subjects' basic characteristics (including demographics, life history, medical history, and medication history);
- ◆ Discontinuations;
- ◆ Summary of adverse events (of all causes and treatment-related);
- ◆ Incidence and severity of adverse events (of all causes and treatment-related);
- ◆ Summary of serious adverse events;
- ◆ Causality analysis of adverse events;
- ◆ Occurrence of abnormal laboratory measurements, vital signs, and ECG data.

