### **11.4.7 Other safety data**

Examinations such as echocardiography, virology, fecal occult blood, pregnancy, and coagulation function will be listed.

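### The SAP's laboratory summaries omit thyroid and coagulation function, so new abnormality in two protocol-named safety panels is not tabulated unless it is recorded as an adverse event

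*SAP*

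**What the plan says.** **Protocol.**
- Section 7.2.1 defines the laboratory safety parameters as "laboratory tests (hematology, urinalysis, blood biochemistry, thyroid function, and coagulation function".
- Section 2.2 makes this a secondary endpoint: "Incidence and severity of adverse events (AEs) and serious adverse events (SAEs), vital signs, ECG, and laboratory abnormalities". No panel is excepted.
- The synopsis, under safety analysis, states: "Laboratory tests that are normal before the study but become abnormal after starting treatment will be described".
- Section 8.4.3 includes among the planned descriptive summaries: "Occurrence of abnormal laboratory measurements, vital signs, and ECG data". It then hands the detail over: "The specific analysis is described in the statistical analysis plan".
- Both panels are measured repeatedly. For thyroid, Schedule of Activities note 12 reads: "The thyroid function is evaluated within 7 days prior to the first dose, before drug administration on Day 1 of every two cycles", followed by end of treatment and the first safety follow-up visit. Note 11 schedules coagulation at screening, every cycle, end of treatment and the first safety follow-up visit.

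**SAP.**
- Section 11.4.2 gives a by-visit summary of values and changes from baseline for hematology, blood biochemistry and urinalysis. For the same three panels it then states: "The hematology, blood biochemistry, and urinalysis of each cohort will be summarized by the normal/abnormal changes before and after treatment". It also lists all laboratory results by subject, with abnormal values marked.
- Section 11.4.7 states: "Examinations such as echocardiography, virology, fecal occult blood, pregnancy, and coagulation function will be listed".
- TSH, T3, T4 and thyroid function are not mentioned anywhere in the SAP.

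**The concern.** The protocol leaves the specific safety analysis to the SAP, so the SAP is where a reader expects each protocol-named laboratory panel to be summarized. It covers three of five without saying why. A listing shows individual values but gives no incidence, while the protocol's endpoint and synopsis ask about the occurrence of abnormality and about change from normal to abnormal.

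Thyroid function is the more consequential omission. The protocol itself reports hypothyroidism and hyperthyroidism as reactions to SHR-1210 (section 1.1.1.5) and gives treatment-related hypothyroidism as 5.6% in 539 treated patients (section 1.3.1). Appendix 4 has a separate row for TSH elevation without symptoms, so the protocol expects biochemical change that may never become a reported event. If the SAP is followed as written, the study report need not contain a count of subjects in each cohort whose thyroid or coagulation tests became abnormal on treatment.

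**Working it through.** No sample size, power or error-rate calculation applies. The check sets the protocol's panel list against the SAP's outputs.

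| Panel (Protocol 7.2.1) | By-visit values and change (SAP 11.4.2) | Normal/abnormal change (SAP 11.4.2) | Listing |
|---|---|---|---|
| Hematology | yes | yes | yes |
| Blood biochemistry | yes | yes | yes |
| Urinalysis | yes | yes | yes |
| Coagulation function | no | no | yes (11.4.2 and 11.4.7) |
| Thyroid function | no | no | yes (11.4.2, through the all-results listing) |

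Panels without a specified summary: 5 − 3 = 2. In parameters, using Schedule of Activities notes 11 and 12, that is 3 for thyroid (TSH, FT3, FT4) plus 5 for coagulation (APTT, PT, TT, FIB, INR), or 3 + 5 = 8.

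**Does another part of the SAP fill the gap?**

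1. *General default (SAP section 11).* Unless stated otherwise, all data are summarized descriptively. For coagulation, 11.4.7 does state otherwise. For thyroid, the default could yield means, medians and ranges, or frequencies. It specifies no change from baseline and no normal/abnormal change, and the latter is what the synopsis undertakes to describe.
2. *Adverse event tables (SAP 11.4.1).* These count an abnormality once it is recorded as an AE. Protocol 7.2.2 counts laboratory findings as AEs when they are clinically significant, so an abnormality not judged significant need not appear there.
3. *Immune-related and special-interest tables.* Under Protocol 7.2.7, thyroid events fall in the category of other immune-related AEs, which requires Grade 3 or above. In Protocol Table 11, the row for hypothyroidism and thyroiditis contains only acute and autoimmune thyroiditis as preferred terms. A coded hypothyroidism event would appear in the overall TEAE table but may not reach the immune-related one.

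**Why change from baseline is needed.** Inclusion criterion 8(i) admits a subject with abnormal TSH if T3 and T4 are normal. Criterion 8(g) admits PT and APTT up to 1.5 × ULN. Some subjects can therefore start outside the normal range on either panel. A count of on-treatment abnormal values alone would mix existing with new abnormality; the baseline comparison already used for the other three panels separates them.

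**Is the reduction declared?** SAP section 2 records added exploratory analyses (OS, TTOR, subgroups) and says nothing about laboratory panels. SAP 9.2 takes laboratory data as a safety endpoint in line with the protocol, again without excluding a panel.

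**The case against.** The best case for leaving the SAP alone has four parts.

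- **Nothing is hidden.** Every laboratory result is listed, with abnormal values marked and their clinical significance indicated. This stands. A reader might infer that thyroid and coagulation results go unreported, or that biochemical dysfunction is missed altogether; the documents do not support that. What is missing is the aggregate count.
- **The default covers thyroid.** The general rule in SAP section 11 could produce a descriptive thyroid summary. This stands in part: it would be wrong to say that thyroid data will certainly appear in no table. But the rule names no panel and does not supply the normal-to-abnormal comparison, and it does not help coagulation.
- **Clinically relevant changes reach the AE tables.** Largely true. SAP 11.4.1 includes laboratory abnormality in its AE definition, and TEAEs are tabulated by system organ class, preferred term and grade. The remaining gap is mainly abnormality not judged clinically significant.
- **The protocol promised no specific tables.** Section 7.2.1 lists parameters and 8.4.3 defers to the SAP. That is fair as regards table layout. The synopsis statement on tests that become abnormal is nevertheless general, and the SAP implements it for only some of the tests.

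Two further inferences are tempting and should not be drawn. One is a number of subjects whose thyroid dysfunction would go uncounted. The documents give no rate of on-treatment TSH abnormality; the 5.6% is treatment-related hypothyroidism as an AE, pooled over patients given SHR-1210 alone or with other drugs. The other is that missing coagulation tables would conceal apatinib-related bleeding. The documents report hemorrhage as adverse events, which the TEAE tables capture, and do not tie it to shifts in APTT, PT or INR.

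**Conclusion.** The point holds as a gap in descriptive safety reporting. Two of the five laboratory panels named in Protocol 7.2.1, comprising eight parameters, have no specified summary of change from baseline or of normal/abnormal change. Coagulation is explicitly listing-only. Thyroid function is unnamed and has, at most, the generic default. As written, the incidence of new abnormality in either panel is not tabulated unless it is recorded as an AE.

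This rests on two readings: that laboratory abnormalities in the secondary endpoint and in the synopsis mean all the laboratory panels in 7.2.1, and that the three panels named in SAP 11.4.2 are the complete set for those tables. Neither text limits or extends its scope otherwise.

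The number of subjects affected cannot be estimated from the documents. The primary ORR analysis, the two-stage decision rules and the error rates do not depend on this. It is worth correcting because it concerns part of a secondary endpoint and the correction is nearly free.

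**What to change.** In SAP 11.4.2, add thyroid function (TSH, FT3 and FT4, or T3 and T4 where the protocol's substitution was used) and coagulation function (APTT, PT, INR, TT, FIB) to both existing summaries: by-visit values with change from baseline, and normal/abnormal change before and after treatment. Keep the baseline definition already in that section. Thyroid visits follow the two-cycle schedule. Show free and total hormone values separately, since they are different measurements. Delete coagulation function from the listing-only sentence in SAP 11.4.7.

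A low/normal/high split for thyroid would show the direction of change, but it goes beyond what the SAP does for its other panels and is optional. If a listing was the deliberate choice for either panel, the SAP should say so and give the reason.

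Cost: two more panels in existing table shells. Both are already scheduled, and Protocol 12.1.2 already requires laboratory results in the eCRF, so no visit, sample or procedure changes.

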### **11.4.3 Vital signs**

The vital sign baseline is defined as the last sign result tested before the first administration.

The vital signs of each cohort will be summarized by visit using descriptive statistics. At the same time, the changes from baseline will also be summarized and analyzed by descriptive statistics.

All vital signs will be listed.

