# 11 STATISTICAL ANALYSIS

The statistical analysis involved in this study will be carried out in accordance with cohorts. The statistical analysis plan must be finalized before database locking. Statistical tables, listings, and figures will be generated using SAS (v9.4).

In this study, unless otherwise stated, all data will be summarized using descriptive statistics in accordance with the following general principles.

Measurement data will be summarized by mean, standard deviation, median, maximum, and minimum. The decimal places of minimum and maximum should be consistent with those recorded on the CRF, mean and median have one more decimal place than those of the raw data, and the standard deviation has 2 more decimal places than that of the raw data. Count data will be summarized by frequency and percentage; categorical variables will be statistically described using the frequency and percentage of each category, with one decimal place rounded for percentages.

Time-to-event data will adopt the Kaplan-Meier method to estimate survival rates and plot survival curves; serum concentration data will be summarized using geometric mean, geometric standard deviation, geometric coefficient of variation, mean, standard deviation, coefficient of variation, median, maximum, and minimum.

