### **11.4.4 Physical examination**

The physical examination baseline is defined as the last examination result before the first administration.

The physical examination will be summarized by the normal/abnormal changes before and after treatment.

The abnormal results of physical examination will be listed.

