### **11.4.5 12-Lead ECG**

Baseline is defined as the most recent test data before the first dose.

Items concerning ECG include: HR (times/min), PR interval (ms), QT interval (ms), and QTc (ms). The measured value and change from baseline of each ECG variable at each time point will be summarized using descriptive statistics. At the same time, ECG will be summarized by the normal/abnormal changes before and after treatment.

If QTcF is not directly provided on the ECG report, it will be obtained using the following formula (Fridericia formula):

$$QTcF = QT/(RR^{1/3})$$

RR = 60/heart rate (s)

Related data will also be reported in the form of listing.

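### SAP 11.4.3 plans no count of subjects with abnormal vital signs, although Protocol 8.4.3, on its natural reading, lists that occurrence as a safety output (minor)

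*SAP*

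**What the plan says.** Protocol 8.4.3 restricts safety reporting to descriptive summaries and lists the outputs. One is "Occurrence of abnormal laboratory measurements, vital signs, and ECG data". The incidence and severity of adverse events is a separate entry in the same list. On method the section says: "The specific analysis is described in the statistical analysis plan".

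SAP 11.4.3 takes the last reading before first administration as baseline and then states: "The vital signs of each cohort will be summarized by visit using descriptive statistics". It adds descriptive statistics for change from baseline and a listing of all values. SAP 11 defines the statistics: "Measurement data will be summarized by mean, standard deviation, median, maximum, and minimum".

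The comparable SAP sections go further:

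- Laboratory tests (11.4.2): "The hematology, blood biochemistry, and urinalysis of each cohort will be summarized by the normal/abnormal changes before and after treatment".
- Physical examination (11.4.4): "The physical examination will be summarized by the normal/abnormal changes before and after treatment".
- ECG (11.4.5), in addition to statistics at each time point: "ECG will be summarized by the normal/abnormal changes before and after treatment".

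**The concern.** An occurrence of abnormal values is a count of subjects, with a percentage. The summaries planned for vital signs describe the distribution of readings at each visit and contain no such count. A programmer who followed the SAP exactly would produce the output named in Protocol 8.4.3 for laboratory tests and ECG, but not for vital signs.

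Blood pressure is the vital sign that matters most here. Protocol 1.1.2 names hypertension among the common apatinib reactions whose incidence differed from placebo. Table 9 in Protocol 5.2.3 requires an apatinib delay and a one-level reduction for Grade 3 hypertension after corrective treatment. Cohort 2 receives apatinib from the start, and cohort 1 receives it after 4-6 cycles if there is no progression. Adverse event tables show raised blood pressure only when an investigator records it as an event. A count of measured values does not depend on that step and would give a reader a partial cross-check.

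**Working it through.** The plan states no figure on this point and no arithmetic applies. The check is a comparison of the texts.

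1. **What is promised.** Protocol 8.4.3 names abnormal laboratory values, vital signs and ECG data in one phrase governed by the word occurrence. Adverse event incidence has its own entry, so adverse event tables do not by themselves discharge this one.

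2. **What SAP 11.4.3 yields.** It yields five statistics per visit, the same for change from baseline, and a listing. None is a number of subjects beyond a limit, and no limit is defined. The laboratory listing in 11.4.2 marks abnormal values; 11.4.3 asks for no such marking.

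3. **Whether the by-visit tables can stand in.** A maximum shows that at least one subject was high at that visit, not how many. Separate visit tables cannot show how many different subjects were ever high. SAP 9.5 brings an unplanned visit into by-visit analyses only when a planned visit or result is missing or invalid, so a high reading at an extra visit may appear in no summary table.

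4. **Whether another SAP section supplies the count.** SAP 11.4.7 covers echocardiography, virology, fecal occult blood, pregnancy and coagulation, by listing only. SAP 11.4.1 counts treatment-emergent adverse events by system organ class and preferred term, takes the highest grade per subject, and separates the two phases of cohort 1. That covers hypertension recorded as an event, not measured values.

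5. **Whether the omission follows a pattern.** ECG intervals and heart rate are continuous measurements, like blood pressure. They receive both descriptive statistics and a normal/abnormal summary. A continuous scale therefore does not explain why vital signs receive only the former.

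Following the SAP as written gives no occurrence of abnormal vital signs.

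**The case against.** The strongest reply is that the commitment is soft. Protocol 8.4.3 asks only for descriptive summaries, sets no threshold or table format, and defers to the SAP. The word *abnormal* could be attached to laboratory measurements alone. The safety paragraph in the synopsis commits to describing normal-to-abnormal change for laboratory tests only. This stands in part: the protocol is not explicit. But the narrow reading leaves an occurrence of vital signs, which has no meaning, and the SAP itself applies normal/abnormal to ECG, the last item in the phrase.

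Second, much of the content is reported elsewhere. Protocol 7.2.2 counts adverse signs and worsening of existing conditions as adverse events, these are tabulated by worst grade, and every vital sign reading is listed. This stands, and it is why the point is minor. A reader might infer that apatinib hypertension would go unreported, or that dose decisions would suffer. The documents do not support either: the adverse event tables cover recorded hypertension, and the dose rule in Table 9 works from the graded toxicity in the individual patient, not from a summary table.

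Third, the cross-check is imperfect. Scheduled on-treatment readings are taken before dosing on Day 1 of each cycle, so they miss rises between visits and hypertension controlled by medication. The two counts can properly differ in either direction. This also stands.

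Fourth, the protocol gives no on-treatment limit for blood pressure. The 140/90 mmHg figure comes from exclusion criterion 13, which concerns hypertension uncontrolled by antihypertensives. That is correct, so any use of it here is a choice the SAP must state.

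**Conclusion.** There is a real but minor misalignment between protocol and SAP. It rests on the natural reading of Protocol 8.4.3, under which *abnormal* applies to all three items. The missing piece is one derived summary of data that are collected and listed; no efficacy, stopping or dose rule is affected.

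The size cannot be given in subjects, because the documents do not say how many will have abnormal readings. A reader might also infer that the secondary endpoint in Protocol 2.2 goes unanalysed, since vital signs appear there. That wording is ambiguous about what is to be counted, and vital signs are summarized, so the conclusion does not extend that far.

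**What to change.** Add to SAP 11.4.3 a normal/abnormal summary of vital signs before and after treatment, by cohort, on the model of 11.4.5. For blood pressure, give the number and percentage of safety-set subjects whose worst post-baseline value, scheduled or unscheduled, exceeds limits written into the SAP before database lock. Systolic > 140 or diastolic > 90 mmHg would serve, as would the grade cut-offs of CTCAE v4.03, the version already used for grading. Cross-tabulate against baseline status by the same limits, because criterion 13 does not guarantee that every subject starts below 140/90. State limits for pulse, respiratory rate and temperature too, since the documents give none. Keep the by-visit tables and the listing.

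A phase split for cohort 1 is optional. It would need a stated baseline for the apatinib phase (11.4.3 defines one only before first administration), a denominator of subjects who started apatinib, and a rule that a reading taken before the first apatinib dose does not count in that phase.

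The cost is one more table and the work of fixing limits; no new data are needed. The table will include isolated readings of no clinical importance, so a footnote should say that it counts measured values, not adverse events.
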